This aim will be accomplished by assessing safety outcomes in patients undergoing remote ischemic preconditioning treatment. The primary safety endpoint will be all serious adverse events. Secondary safety endpoints will include deep and superficial vein thrombosis and all-cause mortality. Ascertainment that RPreC poses no major excess risk to patients will allow for subsequent efficacy testing in a larger clinical trial.

A.3. Specific Aim 3: Signals of Efficacy

To employ imaging biomarkers to demonstrate biologic efficacy of remote ischemic preconditioning as a sustained therapy for prevention of ischemic brain injury from cerebral small vessel disease, and to employ cognitive, ambulation, and clinical stroke event outcome measures to explore potential clinical efficacy.

This aim will be accomplished by measuring volumetric progression of white matter ischemic injury on magnetic resonance imaging (biomarker efficacy) and cognitive battery performance,

ecologic ambulation assessment, and recurrent stroke events (clinical efficacy). MRIs will be performed at baseline and at 1 year (end of randomized phase) and several markers of injury progression assessed, including FLAIR hyperintensity volumetric burden (primary biomarker efficacy outcome), diffusion tensor imaging volumetric burden, and cerebral atrophy. Wireless sensors will be used to assess gait quantity and quality in real-world activity at baseline and 1 year. A cognitive battery sensitive to executive, attentional, and memory function, reflecting subcortical-frontal system integrity, will assess progression of vascular cognitive impairment. Lastly, clinical events during the year of randomized therapy will be compared across treatment arms, including ischemic stroke, transient ischemic attack, hemorrhagic stroke, myocardial infarction, and cardiovascular death.

C. Trial Design

C.1. Study Overview

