Following the randomization assignment, all patients will have follow-up visits at 1, 3, 6, 9, and 12 months. Feasibility, safety, and efficacy assessments will be performed at each of these visits, with the 12 month measures, at the conclusion of the randomized phase, constituting the primary outcome timepoint. In addition, the 20 control patients will have follow-up visits at 18 and 24 months, during the period of their delayed start therapy. The cognitive assessment battery will be performed at the first qualifying visit to familiarize participants with the system before the baseline assessment at randomization and additionally at 1 month to assess whether any cognitive changes accompanied the initial RPreC effect. If participants ceased study treatment during the study, they will be encouraged to continue attending follow-up visits; all withdrawn participants will be invited to attend the closeout visit to reduce loss to follow-up.

C.10. Treatment Evaluation

C.10.1. Baseline Evaluation

At study entry, enrolling investigator to record:

- Demographic data (age, sex, vascular risk factors)
- Heart rate
- Blood pressure
- Visual inspection of skin in arms, motor and sensory examinations of the hand
- NIH Stroke Scale (NIHSS)
- Modified Rankin Scale (mRS)
- Barthel Index (BI)
- EQ-5D (health-related quality of life)
- Questionaire to verify stroke free status
- Neurocognitive battery
- MR imaging will be reviewed
- Eligibility for enrollment
- Review informed consent with patient

C. 10.2. Day 30 Evaluation

- Interval Events Form
- Concomitant therapies form
- Heart rate
- Blood pressure
- Visual inspection of skin in arms, motor and sensory examinations of the hand
- NIH Stroke Scale (NIHSS)
- Modified Rankin Scale (mRS)
- Barthel Index (BI)
- EQ-5D (health-related quality of life)
- Questionaire to verify stroke free status

- Patient-reported Comfort Rating Scale a 5 point Likert scale reflecting patient report of subjective experience of RPreC (very comfortable, comfortable, average, uncomfortable, very uncomfortable) (Wang X, Maurin M. Discomfort/Comfort assessment using an ordered category scale.)
- Number of completed 5-minute cycles of RIPC
- Neurocognitive battery

C. 10.3. Month 3, 6, and 9 Evaluations

- Interval Events Form
- Concomitant therapies form
- Heart rate
- Blood pressure
- Visual inspection of skin in arms, motor and sensory examinations of the hand
- NIH Stroke Scale (NIHSS)
- Modified Rankin Scale (mRS)
- Barthel Index (BI)

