- EQ-5D (health-related quality of life)
- Questionaire to verify stroke free status
- Patient-reported Comfort Rating Scale a 5 point Likert scale reflecting patient report of subjective experience of RPreC (very comfortable, comfortable, average, uncomfortable, very uncomfortable) (Wang X, Maurin M. Discomfort/Comfort assessment using an ordered category scale.)
- Number of completed 5-minute cycles of RIPC
- Neurocognitive battery
- Accelerometer assessment of ecologic gait and activity

C. 10.4. Year 1 Evaluation

- Interval Events Form
- Concomitant therapies form
- Heart rate
- Blood pressure
- Visual inspection of skin in arms, motor and sensory examinations of the hand
- NIH Stroke Scale (NIHSS)
- Modified Rankin Scale (mRS)
- Barthel Index (BI)
- EQ-5D (health-related quality of life)
- Questionaire to verify stroke free status
- Patient-reported Comfort Rating Scale a 5 point Likert scale reflecting patient report of subjective experience of RPreC (very comfortable, comfortable, average, uncomfortable, very uncomfortable) (Wang X, Maurin M. Discomfort/Comfort assessment using an ordered category scale.)
- Number of completed 5-minute cycles of RIPC
- Neurocognitive battery
- Accelerometer assessment of ecologic gait and activity
- MR imaging

In the control group, additional evaluations will be performed at 18 months (same as 6 month visit) and 24 months (same as 12 month visit).

Neurocognitive Battery: The tests performed in the neurocognitive battery are: Montreal Cognitive Assessment (MOCA), Trail Making Test (TMT), Phonemic Fluency (Controlled Oral Word Association Test), Semantic Fluency (Animal Naming), Digit Symbol Coding from the Wechsler Adult Intelligence Scale, Third Edition, Hopkins Verbal Learning Test, Center for the Epidemiological Studies-Depression Scale, Neuropsychiatric Inventory, Questionnaire Version (NPI-Q), Mini Mental Status Exam. These tests are well standardized in the literature and can be administered by study coordinators after training from a clinical neuropsychologist. The test battery has been selected for tests sensitive to attentional, executive, and memory impairments particularly affected by subcortical vascular disease ⁵.

MR imaging: Sequences performed will include FLAIR, volumetric T1, GRE, diffusion tensor imaging (DTI) and arterial spin labeled (ASL). The total table acquisition time will be 18 minutes.

Measurement of Volumetric MRI Assessment:

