To ensure that appropriate ethical consideration is given to the welfare of the patients enrolled in the study, a Data and Safety Monitoring Board (DSMB) will oversee the trial. The DSMB will review the incidences and circumstances of adverse events that occur during the course of the trial. Formal interim analysis will occur at the half way -point, after enrolled patients have completed 50% of patient months of follow up. If the incidence of recurrent stroke or all serious adverse events is higher in the combined device arm than the control arm the study will be placed on hold. The DSMB will conduct a detailed analysis of the safety data. The DSMB may recommend making changes it deems necessary in the interests of the safety or well-being of the study subjects, or suspending or stopping the study. Final determination of a formal stopping rule will be the prerogative of the appointed DSMB.

The members of the DSMB are:

[name], Stroke Neurologist, University of Southern California [name], Stroke Neurologist, Rancho Los Amigos National Rehabilitation Center

C. 14.2. Statistical Design and Analysis Plan

The demographic and baseline clinical characteristics of the study population will be delineated with standard descriptive statistics. Categorical variables describing the clinical history, examination findings, and initial treatment will be summarized by frequencies. Continuous variables such as vital signs, laboratory results, and time variables that follow normal distribution

will be characterized by means, standard deviations, and 95% confidence intervals (CI). Ordinal and non-normally distributed variables (such as the NIHSS) will be characterized by medians and interquartile ranges. RIPC and control patients will be compared to delineate covariate balance. Wilcoxon Rank-Sum tests will be used for continuous or ordinal variables; Fisher's exact tests and chi-square tests will be used for grouped or nominal categorical variables. Comparisons of changes across time (i.e. base to one year) within and between groups will be made using repeated measure analysis variance methods or the non-parametric analog.

C. 14.3. Selection and Analysis of Endpoints

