Additional efficacy endpoints explored will include accelerometer assessment of gait quantity and quality in real-world activity; z scores on individual tests and summed performance on the cognitive battery, and incident ischemic stroke, transient ischemic attack, hemorrhagic stroke, myocardial infarction, and cardiovascular death. To protect against bias in ascertainment of the recurrent stroke secondary endpoint, analysis to include a) adjudication of potential endpoint stroke events by 2 independent blinded neurologists (preventing rater bias), and b) administration of the Questionnaire to Verify Stroke Free Status at each follow-up visit, to trigger endpoint evaluations (preventing ascertainment bias).

C.14.4. Sample Size Calculations

Subject size is typical sample size for a feasibility study with a device. We are looking at adherence in order to plan a larger phase II/III successor trial.

Sample Size Justification

The primary feasibility and study endpoint is RPreC adherence at 12 months. As we do not expect clinically important differences in adherence among the three groups, it may be possible to combine two or all three groups. In this study, we also wish to test the null hypothesis that the true adherence is at least 75%. The table below gives the lower 90% or 95% confidence bound for 90%, 95% or 100% observed adherence as a function of sample size and the corresponding statistical power for testing the null hypothesis that the true population adherence is 75% versus the one sided alternative of greater than 75%. The current study is not necessarily sufficiently powered for any of the safety or efficacy outcomes. Therefore this is a pilot study in terms of safety and efficacy.

Lower 90% or 95% one sided confidence bound for true adherence

| | adherence=90% | | adherence=95% | | adherence=100% | |
|----|---------------|------------|---------------|------------|----------------|----------------|
| | 90% | 95% | 90% | 95% | | |
| Ν | confidence | confidence | confidence | confidence | 90% confidence | 95% confidence |
| 20 | 75.5% | 71.8% | 81.9% | 78.5% | 89.1% | 86.1% |
| 40 | 81.0% | 78.5% | 87.2% | 85.1% | 94.4% | 92.8% |
| 60 | 83.1% | 81.2% | 89.2% | 87.6% | 96.2% | 95.1% |

Power for one sided test against null hypothesis of 75% vs > 75%

| | adherence=90% | | adherence=95% | | adherence=100% | |
|----|---------------|------------|---------------|------------|----------------|------------|

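### The C.10.1 baseline list omits the gait accelerometer that Aim 3 requires at baseline, so following the visit lists leaves no baseline for the planned change analysis of this exploratory endpoint

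*Combined protocol and SAP*

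**What the plan says.** All references are to the combined protocol and SAP.

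- **Aim 3 (A.3), gait:** "Wireless sensors will be used to assess gait quantity and quality in real-world activity at baseline and 1 year".
- **Aim 3 (A.3), MRI:** "MRIs will be performed at baseline and at 1 year (end of randomized phase".
- **C.10.1, Baseline Evaluation:** the list opens with "At study entry, enrolling investigator to record" and has 13 items. None is an accelerometer or gait measure. The only imaging item is "MR imaging will be reviewed".
- **C.10.2, Day 30:** no accelerometer item.
- **C.10.3 (Months 3, 6 and 9) and C.10.4 (Year 1):** both include "Accelerometer assessment of ecologic gait and activity". C.10.4 also lists MR imaging as a procedure.
- **Control group, Year 2 (end of the C.10.4 list):** "additional evaluations will be performed at 18 months (same as 6 month visit) and 24 months", the latter repeating the 12-month visit.
- **C.14.2, analysis:** "Comparisons of changes across time (i.e. base to one year) within and between groups" are to be made by repeated-measures analysis of variance or a non-parametric analog.
- **C.14.3, endpoints:** "Additional efficacy endpoints explored will include accelerometer assessment of gait quantity and quality in real-world activity". No timing is given there.

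**The concern.** Aim 3 promises a baseline gait measurement and C.14.2 needs one, but the list that staff would use at study entry does not ask for it. A baseline value that was not collected cannot be recovered later.

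Month 3, the first listed accelerometer visit, falls about three months into device treatment. It is a poor substitute baseline, because a change measured from Month 3 discards whatever effect is already present by then. If the effect built up linearly over the year (an assumption), change from Month 3 would keep (12 − 3)/12 = 75% of it.

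At stake are the within-group and between-group change analyses of gait, one of the exploratory efficacy signals in Aim 3. The imaging line in the same list raises a lesser question: it mentions review where Aim 3 has a scan performed.

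**Working it through.** **Number of patients affected.** The plan gives two allocation statements, and both yield the same arm sizes:

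- 2:1 (A and C.3): 60 × 2/3 = 40 device, 20 control. This reproduces the 40 stated in C.3.
- 1:1:1 (C.1): 2 × 60/3 = 40 device, 20 control.

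**Accelerometer items by visit, from the C.10 lists.** Baseline 0, Day 30 0, Months 3, 6 and 9 one each, Month 12 one. Section C.9 ties its efficacy assessments to the follow-up visits at 1, 3, 6, 9 and 12 months, so it does not supply a baseline gait value. Under C.6, device treatment follows randomisation. With the lists followed as written:

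- patients with a baseline gait value: 0 of 60;
- device patients with a gait value from before randomised treatment: 0 of 40;
- controls: no baseline at randomisation, but their Month 3 to 12 values precede their Year 2 treatment.

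**Cost in precision.** The documents give no correlation between baseline and 12-month gait, so I assume ρ = 0.5, 0.7 or 0.9, with equal variances at the two times. Taking the variance of a 12-month-only comparison as 1:

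- change score (what the planned comparison amounts to with two time points): 2(1 − ρ) = 1.0, 0.6, 0.2;
- baseline as covariate: 1 − ρ² = 0.75, 0.51, 0.19.

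The inverse of each is the variance ratio incurred by having only the 12-month value.

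The detectable difference for a two-sample t-test, 40 against 20, two-sided 5%, 80% power, is 0.780 SD of the 12-month value. As a check, the normal approximation gives (1.960 + 0.842) × √(1/40 + 1/20) = 0.767. Multiplying 0.780 by the square root of each relative variance gives the detectable differences when a baseline exists:

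| Assumed ρ | Ratio against change score | Detectable, change score | Ratio against covariate model | Detectable, covariate model |
|---|---|---|---|---|
| 0.5 | 1.0 | 0.78 SD | 1.33 | 0.68 SD |
| 0.7 | 1.67 | 0.60 SD | 1.96 | 0.56 SD |
| 0.9 | 5.0 | 0.35 SD | 5.26 | 0.34 SD |

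Without a baseline the figure is 0.78 SD throughout.

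**Covariate model against change score.** (1 − ρ²)/[2(1 − ρ)] = (1 + ρ)/2 = 0.75, 0.85, 0.95. The covariate model therefore has the smaller variance at each assumed correlation. This holds for any continuous outcome with a baseline value, not only gait.

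**The plan's power table (C.14.4).** It concerns adherence only. An exact binomial test reproduces its entries for 90% and 95% adherence to within 0.001. No gait or MRI quantity enters it.

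**The case against.** Aim 3 is operative text and does require baseline gait. C.10.1 omits the item but does not forbid it, and the C.10 lists are not exhaustive: the familiarisation run of the cognitive battery (C.9) and the device tolerance session (C.8) are not itemised in C.10.1 either. Figure 5 is not shown in the text available and may place the assessment correctly. This stands in part. The counts of 0 of 60 and 0 of 40 hold only if staff follow the lists over Aim 3. Even so, the two text sections disagree, and the visit list is what staff would work from.

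The precision loss should be judged first against the analysis that the plan specifies. That also stands: against the planned change analysis there is no loss at ρ = 0.5. The larger ratios apply only if the covariate model is adopted.

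A reader might infer three stronger things:

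- **That no baseline MRI is planned, or that the eligibility scan will serve as the endpoint baseline.** The documents do not support this. Aim 3 has MRIs performed at baseline, the volumetric MRI section puts all participants on one scanner, and no text makes the eligibility scan the baseline. The review item in C.10.1 is compatible with acquiring a study scan and then reading it.
- **That the gait comparison between arms becomes invalid.** It does not. The 12-month values are still compared between randomised groups.
- **That the trial's main conclusion is at risk.** It is not. C.11 says the primary endpoint does not draw on the control group, and C.14.4 already describes the study as a pilot for safety and efficacy.

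**Conclusion.** The gait omission is real. A.3 and C.10.1 disagree, and if the C.10 lists are followed with full enrolment, none of the 60 patients has a baseline gait value and none of the 40 device patients has one from before randomised treatment. Change from baseline in gait, which C.14.2 needs, then cannot be computed in either group.

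The consequence is limited to an exploratory endpoint. How much precision is lost depends on an unknown correlation: from nothing to a fivefold variance against the planned change analysis over the assumed range. The imaging line is an ambiguity in wording only. This should be corrected because the correction is simple and the measurement is already promised; it does not call the design into question.

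**What to change.** 1. **Add the gait item to C.10.1**, worded as in the later lists ("Accelerometer assessment of ecologic gait and activity"), to be done before randomisation and, where feasible, before the C.8 device session, since every consenting patient has that session before allocation. Check that Figure 5 agrees. Cost: at least 60 sessions on top of the 4 × 60 = 240 already listed for Year 1, and more if patients who later fail screening are measured.
2. **Clarify the imaging item in the same edit.** List acquisition of the baseline study-protocol MRI separately from review of the eligibility scan, so that C.10.1 matches Aim 3. This is wording only, because the scan is already called for.
3. **In C.14.2, replace change comparisons with a model that has the baseline value as covariate** for continuous 12-month outcomes that have a baseline: cognitive z scores, mean white matter hyperintensity volume, DTI measures and atrophy, with gait added once its baseline is collected. Use a rank-based version where the data are skewed. This needs no extra data for outcomes already measured at baseline. It does not apply to the binary lead MRI endpoint.

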All participating investigators and site personnel that will be performing the autoRIC procedure will be trained in the use of the study device prior to participating in the study. Device training will be conducted by the Principal Investigator. Training will be done according to the autoRIC User Manual and will include instructions on charging the device prior to the first use, recharging the device after each procedure, verifying the device is charged prior to each procedure, recognizing and addressing the different Warning/Error indications (e.g., battery light flashing blue, indicating that the battery is low but can still perform at least one procedure, battery light steady red, indicating battery low error – not enough battery power to run a complete procedure, etc.) and specific instructions for returning the device to the sponsor in the event of an error notification that cannot be addressed by the site personnel, or a failure of the device to charge after three hours.

All device training will be documented in a training log that will be maintained in the site regulatory binder.

C.3. Subjects

60 subjects will be identified prior to discharge from the inpatient Stroke Service, which manages over 350 patients yearly, and from the inpatient rehabilitation unit that cares for 100 patients yearly with disabling stroke. They will also be identified in our outpatient stroke clinic that manages over 500 patients yearly. Based upon a review of the past 5 years of stroke patients evaluated, we anticipate that at least 20% are likely to be eligible. Potential participants will be approached by an investigator and given the informed consent from to review. Enrolled subjects will be randomized 2:1 to active treatment (40 patients) and control (20 patients).

C.3.1.Entry Criteria

To enter the study screening phase, patients must meet all of the following inclusion and exclusion criteria:

Inclusion Criteria

I. Clinical

- 1. Clinical lacunar stroke syndrome within the past 6 months (from among the following 12 syndromes as per SPS3 criteria: pure motor hemiparesis (PMH), pure sensory stroke, sensorimotor stroke, ataxic hemiparesis, dysarthria-clumsy hand syndrome, hemiballism, PMH with facial sparing, PMH with horizontal gaze palsy, PMH with contralateral III palsy, PMH with contralateral VI palsy, cerebellar ataxia with contralateral III palsy, pure dysarthria)
- 2. Absence of signs or symptoms of cortical dysfunction

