- 3. No proximal large vessel atherosclerosis, intracranial atherosclerosis or cerebellar stroke.
- 4. No major cardioembolic source requiring anticoagulation or other specific therapy

II. Imaging

- 1. MRI presence of a small subcortical ischemic per SPS criteria, any 1 or more of:
 - a. Diffusion-weighted imaging lesion < 2.0cm in size at largest dimension and corresponding to the clinical syndrome.
 - b. Well delineated focal hyperintensity <2.0 cm in size at largest dimension (including rostro-caudal extent) on FLAIR or T2 and clearly corresponding to the clinical syndrome. If other focal hyperintensities are present, the case will be discussed with the PI prior to randomization
 - c. Multiple (at least 2) hypointense lesions of size 0.3-1.5 cm at largest dimension (including rostro-caudal extent) only in the cerebral hemispheres on FLAIR or T1 in patients whose qualifying event is clinically hemispheric
 - d. Well delinated hypointense lesion <1.5 cm in size at the largest dimension (including rostro-caudal extent) on FLAIR or T1 corresponding to the clinical syndrome. MRI must be done at least 1 months after the qualifying stroke
- 2. Absence of cortical stroke and large (> 1.5cm) subcortical stroke, recent or remote
- 3. White matter hyperintensity score of 2 (moderate) or 3 (severe) on the European Scale of Age-Related White Matter Change
- 4. No evidence of cerebral amyloid angiopathy as per Boston Criteria.

Exclusion Criteria

To be eligible for entry into the study, none of the following criteria may be present:

- 1. Disabling stroke (Rankin Scale \geq 4)
- 2. Previous intracranial hemorrhage (excluding traumatic) or hemorrhagic stroke
- 3. Age under 40 years
- 4. High risk of bleeding (e.g. recurrent GI or GU bleeding, active peptic ulcer disease, etc.)
- 5. Anticipated requirement for long term use of anticoagulants (e.g. recurrent DVT)
- 6. Prior cortical or retinal stroke (diagnosed either clinically or by neuroimaging), or other prior cortical or retinal TIA
- 7. Prior ipsilateral carotid endarterectomy
- 8. Impaired renal function: estimated GFR <40

- 9. Patients treated with hemodialysis
- 10. Intolerance or contraindications to aspirin or clopidogrel (including thrombocytopenia, prolonged INR)
- 11. Mini Mental Status Exam score < 24 (adjusted for age and education)
- 12. Medical contraindication to MRI
- 13. Pregnancy or women of child-bearing age who are not following an effective method of contraception

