All participants will undergo a 1.5-Tesla MRI scanning on the same Magnetom scanner. (Siemens, Erlangen, Germany). The protocol will include the following whole brain scans: 3D T1 MPRAGE imaging (TR/TE/TI 2250/3.68/850 ms; flip angle15°; voxel size $1.0 \times 1.0 \times 1.0 \times 1.0$ mm); FLAIR pulse sequences (TR/TE/TI 9000/84/2200 ms; voxel size $1.0 \times 1.2 \times 5.0$ mm, interslice gap 1 mm); DTI (TR/TE 10100/93 ms; voxel size $2.5 \times 2.5 \times 2.5$ mm; 4 unweighted scans, 30 diffusion weighted scans with b-value 900 s/mm²). The complete protocol is estimated to take 35 min.

White matter signal hyperintensities in both supra and infratentorial regions on FLAIR scans, which were not, or only faintly, hypo-intense on T1 weighted images, will be considered WML, except for gliosis surrounding infarcts. WML will be manually segmented on FLAIR images by two trained raters. Total WML volume will be calculated by summing the segmented areas multiplied by slice thickness. Lacunar infarcts were defined as hypo-intense areas with a diameter > 2 mm and < 15 mm with low signal intensity on T1 and FLAIR, ruling out enlarged perivascular spaces and infraputaminal pseudolacunes ⁶. All imaging analyses will be performed by raters blinded to clinical information.

Normalization parameters to the ICBM152 linear template (as provided with SPM5; Wellcome Department of Cognitive Neurology, University College London, UK) and gray (GM) and white matter (WM) tissue and cerebrospinal fluid (CSF) probability maps will be computed by using SPM5 unified segmentation routines on the T1 MPRAGE images ⁷[. Total GM, WM and CSF volumes will be calculated by summing all voxel volumes that had a p > 0.5 for belonging to the tissue class. Total brain volume (TBV) will be taken as the sum of total GM and WM. Intracranial volume (ICV) is a summation of all tissue classes, i.e. total GM, total WM and CSF volume. To normalize for head size, TBV will be expressed as percentage of total ICV.

Co-registration parameters of the FLAIR image to the T1 image will be computed (SPM5 mutual information co-registration) and used to bring both the FLAIR and WML segmentation images into the subject's (anatomical) reference frame. Transformed images will be visually checked for

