Feasibility: Because the primary aim of this trial is assessing feasibility and tolerability, the primary endpoints are descriptive statistics describing the implementation of the RPreC procedure, including behavioral adherence to treatment, physiologic attainment of limb ischemia, and patient self-reported comfort-discomfort during treatment. The simplicity of these endpoints reduces the likelihood of problems in the analysis and interpretation of these endpoints. The procedure will be considered adequately feasible if adherence and physiologic targets are attained in 75% or more of cases. At this early stage of development, observations and lessons from individual cases may warrant procedural protocol changes to optimize the intervention. Such flexible, developmental iterations of the intervention will be closely discussed with, and supervised by, the study DSMB.

Safety: The lead safety endpoint will be all serious adverse events. Secondary safety endpoints will be deep and superficial vein thrombosis and all cause mortality.

Efficacy: The lead efficacy endpoint will be volumetric progression of white matter ischemic injury on magnetic resonance imaging (biomarker efficacy). The primary MRI endpoint will be the proportion of patients with increase in total white matter hyperintensity volume (as percent of total brain volume) above 1.0%. (This value represents the threshold for the upper quintile of progression in the SCOPE trial. Proportion of patients with progression in the upper quintile was the most sensitive MR endpoint analyzed in the SCOPE substudy.) Additional MRI endpoints analyzed will include mean progression total white matter hyperintensity, mean and quintile progression in deep white matter hyperintensity, progression in total brain atrophy, and progression in DTI anisotropy. The MR imaging measures of white matter injury progression, ascertained by automated analysis and blinded readers, are not subject to bias.

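### The white matter lesion rule can count a recent qualifying infarct at baseline and drop it at 12 months, which partly offsets measured progression on the lead MRI endpoint

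*Combined protocol and SAP*

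**What the plan says.** **Lesion rule (C.10, Measurement of Volumetric MRI Assessment).** FLAIR white matter hyperintensities "which were not, or only faintly, hypo-intense on T1 weighted images, will be considered WML, except for gliosis surrounding infarcts". The same paragraph states: "Lacunar infarcts were defined as hypo-intense areas with a diameter > 2 mm and < 15 mm with low signal intensity on T1 and FLAIR". Two raters segment WML by hand, blinded to clinical information. Nothing tells them to label or mask the qualifying infarct.

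**Entry (C.3.1).** The clinical criterion is "Clinical lacunar stroke syndrome within the past 6 months". Imaging item 1a admits a "Diffusion-weighted imaging lesion < 2.0cm in size at largest dimension and corresponding to the clinical syndrome". Item 1b admits a "Well delineated focal hyperintensity <2.0 cm in size at largest dimension" on FLAIR or T2 that matches the syndrome. Neither sets a minimum time from stroke to scan. Item 1d, for lesions already hypointense, requires at least 1 month. Imaging item 2 separately rules out any subcortical stroke larger than 1.5 cm.

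**Recruitment (C.3).** The text says "60 subjects will be identified prior to discharge from the inpatient Stroke Service", and also names the rehabilitation unit and the outpatient clinic as sources.

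**Endpoint (C.14.3; scan times in A.3).** MRI is done at baseline and 1 year. The primary MRI endpoint is "the proportion of patients with increase in total white matter hyperintensity volume (as percent of total brain volume) above 1.0" percent.

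**The concern.** The rule classifies a lesion by its signal on the day of the scan, and the signal of a recent infarct can change over the following year. A lesion that made the patient eligible can be WML on the first scan and an infarct on the second. The change score then mixes growth of small vessel disease with the evolution of the index stroke, and the second component lowers it.

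The lead efficacy endpoint is a yes/no count above a cut-off, so a patient whose true growth is just above 1.0% can be recorded as a non-progressor. Mean WML progression, an additional endpoint in C.14.3, is lowered directly in each affected patient. C.11 and C.14.3 describe the MRI measures as free of bias because analysis is automated and readers are blinded. Blinding does not deal with a classification that changes as the lesion ages.

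**Working it through.** **1. The plan's own figure.** The 1.0% threshold is taken from the upper quintile of progression in a cited trial. The documents give no inputs for it, so it cannot be reproduced. I read it as percentage points of total brain volume (TBV).

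**2. How C.10 classifies an index infarct lying in white matter.**

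| State of the lesion | T1 | FLAIR | Class under C.10 |
|---|---|---|---|
| Not clearly T1-dark | normal or faintly dark | bright | WML, whole lesion |
| Clearly T1-dark, not cavitated | dark | bright | not WML |
| Cavitated | dark | dark | infarct (2–15 mm); rim excluded as gliosis |

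A lesion in row 1 at baseline and row 3 at 12 months goes from fully counted to not counted. The rim is lost as well, because an infarct is now recognised.

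**3. Lesion volume.** For a sphere of diameter d, V = π × d³ / 6.

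- d = 1.0 cm: 0.52 mL
- d = 1.5 cm (cap in imaging item 2): 1.77 mL
- d = 2.0 cm (limit in items 1a and 1b): 4.19 mL

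**4. Offset as a share of the threshold.** Share = V / (0.01 × TBV). TBV is not in the documents; 1,000–1,200 mL is assumed.

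| d | TBV 1,000 mL | 1,100 mL | 1,200 mL |
|---|---|---|---|
| 1.0 cm | 5.2% | 4.8% | 4.4% |
| 1.5 cm | 17.7% | 16.1% | 14.7% |
| 2.0 cm | 41.9% | 38.1% | 34.9% |

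At 1.5 cm this is 0.15–0.18 percentage points. Widening TBV to 900–1,400 mL gives 13–20% of the threshold.

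**5. Could one lesion offset the whole threshold?** That needs d = (6 × 0.01 × TBV / π)^(1/3), which is 2.67 cm at 1,000 mL and 2.84 cm at 1,200 mL. Both exceed every entry limit.

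**6. Who is misclassified (1.5 cm lesion, TBV 1,100 mL).**

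- True growth 1.10% = 12.1 mL: (12.1 − 1.77) / 1,100 = 0.94%, recorded as a non-progressor.
- True growth 1.20% = 13.2 mL: (13.2 − 1.77) / 1,100 = 1.04%, still a progressor.

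The band at risk is therefore about 1.00% to 1.16%.

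**7. Effect on the progressor share (illustration only).** Suppose 20% truly exceed 1.0%, as an upper quintile implies, and growth is exponential. After a loss of δ points the share is 0.2^(1+δ). For δ = 0.147 to 0.177 this is 15.8% to 15.0% if every patient is affected. If growth is instead normal with SD 0.4–1.0 points, it is 10–16%. If only 25–50% of patients are affected, the exponential case gives 17.5–18.9%. Among 20 controls that is 3.5–3.8 expected progressors instead of 4.

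**The case against.** The case for leaving the rule alone has several good parts.

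- **Not every patient is affected.** Lesions already clearly dark on T1, patients entering by items 1c or 1d, and deep grey matter infarcts fall outside the problem. The documents give neither the share that remains nor how often or how fast such infarcts cavitate. This stands. The entry criteria do provide for both bright and hypointense lesions.
- **Size.** A reader might infer that infarct evolution cancels real progression. Step 5 rules that out for a single eligible lesion measured against the threshold. The 35–42% figures need a 2.0 cm infarct, which imaging item 2 bars even though items 1a and 1b allow up to that size. The 1.5 cm case is the safer one.
- **Arms.** A reader might infer a spurious treatment effect. Allocation is randomised and image readers are blinded, so the error is expected equally in all arms. A chance imbalance is possible, but nothing in the documents shows one.
- **Planning.** A reader might infer that the successor trial would rest on a progression rate that is too low. C.14.4 bases that planning on adherence and calls this a pilot for safety and efficacy.
- **Net direction.** A new bright infarct near month 12 would add to WML. The documents do not allow the two effects to be netted, so the downward direction is established only for affected patients.
- **Estimand.** Removing new infarcts from the main endpoint would redefine what C.14.3 sets out to measure. That is a fair objection, and the fix below does not do it.

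None of this removes the gap: the written rule can count the same lesion on one scan and not on the other.

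**Conclusion.** The concern holds in limited form. Where the qualifying infarct is in white matter, FLAIR-bright and at most faintly T1-dark at baseline, and dark on both sequences at 12 months, C.10 understates WML growth. The lead MRI endpoint is partly offset, by at most 15–18% of its threshold for a 1.5 cm lesion and 4–5% for a 1.0 cm lesion. In practice the rule adds noise and lowers measured progression in affected patients, and it changes the classification only of those near the cut-off.

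The figures assume a spherical lesion, complete loss from WML and a brain volume of 1,000–1,200 mL. The conclusion does not extend to bias between arms or to the primary adherence endpoint. It still merits correction before segmentation starts, because this is the lead efficacy endpoint and the remedy is cheap.

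**What to change.** 1. Amend C.10 so that the qualifying infarct is outlined on the baseline FLAIR and diffusion images. Exclude that mask, with its rim, from WML at both baseline and 12 months, whether the lesion is bright or cavitated.
2. Have the enrolling investigator, who already verifies the small subcortical stroke at eligibility review (C.4), record where the lesion is. Pass the raters the location only, so they stay blinded to allocation and to other clinical information.
3. Report time from stroke to baseline MRI by arm.
4. Add two sensitivity analyses: one with the index lesion included, and one with infarcts new since baseline excluded. The main endpoint otherwise stays as defined.
5. Reconcile the 2.0 cm limits in imaging items 1a and 1b with the 1.5 cm exclusion in imaging item 2, because they set the largest possible error.

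**Cost.** A little extra outlining on scans already planned, with no new scans or staff. A small area of white matter is left out of both scans.
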